### **5.1.2 *Treatment Period and Follow-up***

Participants meeting eligibility criteria during the screening period will enter the treatment period. Approximately 270 participants will be randomized via interactive response technology (IRT) in a 1:1:1 ratio to receive 45 mg BMS-986263 QW, 90 mg BMS-986263 QW, or placebo QW by IV infusion in a double-blind manner.

Participants will be stratified at Randomization by the presence of definite steatohepatitis on biopsy (yes versus no). At least 80% of participants will be required to have definite steatohepatitis on the biopsy used to confirm eligibility. Participants will receive study treatment via IV infusion for a total of 12 weeks. Liver biopsy will be performed at Week 12.

After 12 weeks (Day 85) of treatment or after early treatment discontinuation, participants will enter the 24-week follow-up period, during which participants will not receive investigational treatment. After all participants complete the Follow-up Week 4 visit, the study will be unblinded and analyses of the available Week 12 data will be conducted ([Section 10.4.4](#)). Participants who discontinue study treatment before the Week 11 Visit will have an Early Treatment Termination (ETT) visit and will continue into the 24-week follow-up period.

See the SOA in [Table 2](#) and [Table 3](#) ([Section 2](#)).

### **5.1.3 *DMC and Other External Committees***

This study will utilize an external DMC for the duration of the study. Data summaries and listings will be provided to the DMC to facilitate their assessments at the regularly scheduled times and on an ad hoc basis if needed. The safety review includes SAEs and events of special interest (eg, bone fractures, IRRs, and anaphylaxis), focusing on early signal detection. This study will also utilize an Independent Pathology Review Committee (IPRC) to perform central pathology assessments of the liver biopsy samples to support study eligibility and histological efficacy endpoints analyses.

The DMC and IPRC responsibilities, authorities, and procedures will be documented and followed according to their respective charters.

## **5.2 Number of Participants**

Approximately 270 participants are planned to be randomized in a 1:1:1 ratio to receive 45 mg BMS-986263 QW, 90 mg BMS-986263 QW, or placebo QW by IV infusion for 12 weeks.

## **5.3 End of Study Definition**

The start of the study is defined as the first visit for first participant screened. End of study (EOS) is defined as the last visit or scheduled procedure shown in the SOA ([Section 2](#)) for the last participant. Study completion is defined as the final date on which data for the primary endpoint was or is expected to be collected, if this is not the same. The end of the study for analysis of [REDACTED] samples is included in [REDACTED].

## **5.4 Scientific Rationale for Study Design**

Phase 1b and Phase 2 studies of BMS-986263 enrolled participants with advanced liver fibrosis caused by NASH or HCV. Review of safety data from these studies demonstrated that BMS-986263 was generally safe and well tolerated. Based on efficacy data from the small number of participants in these studies who had advanced liver fibrosis, Study IM025017 will investigate the effects of BMS-986263 in a larger population of participants with compensated cirrhosis due to NASH.

The focus of this placebo-controlled, Phase 2 study is to demonstrate the efficacy, safety, tolerability, PK, [REDACTED] effects of BMS-986263 in participants with compensated cirrhosis due to NASH. The study schematic is provided in [Figure 1](#).

The study will seek to confirm the findings of prior clinical studies demonstrating improvement in fibrosis in participants with advanced liver fibrosis. In this study, BMS-986263 at doses of 45 mg or 90 mg QW for 12 weeks, compared with placebo, will be utilized to assess proof-of-concept of the efficacy (as measured by the improvement of liver fibrosis), safety, and tolerability of BMS-986263 in the study population. The 45 mg and 90 mg doses were chosen because these doses were studied in the prior Phase 2 study of HCV-SVR patients; these doses appeared to be efficacious and were generally safe and well tolerated. A treatment duration of 12 weeks was chosen because an antifibrotic effect was observed after 12 weeks of therapy in that study. The follow-up period will allow assessment (utilizing noninvasive assessments of fibrosis) of the off-treatment durability of efficacy through Follow-up Week 24 (or up to 36 weeks total duration).

Efficacy, safety, PK, [REDACTED] effects will be compared with results from placebo-treated participants and across treatment arms to identify the optimal doses and dosing regimen for future development.

Complete details of the study design are provided in [Section 5](#).

## **5.5 Justification for Dose**

In a Phase 1 single-ascending dose study (ND-L02-s0201-001) in healthy, normal, male participants, dosing was weight-based [REDACTED] BMS-986263 was generally safe and

well tolerated at all dose levels. After IV infusion administration at the dose ranges given above, plasma concentrations of the siRNA component, NDT-05-0038, were consistent over time with an open, [REDACTED] IV infusion model.

The model-predicted values for the primary PK parameters total plasma clearance (CL) and volume of the central compartment were consistent among participants and among doses and a log-log plot of the model-predicted area under the concentration vs time curve extrapolated to infinity vs dose was linear [REDACTED]

[REDACTED]. The mean elimination half-life across [REDACTED] with no apparent dose-related trends. [REDACTED]

In the present study, the doses of 45 mg QW and 90 mg QW BMS-986263 will be investigated in participants with compensated cirrhosis due to NASH. Selection of the doses is based on nonclinical safety data and the clinical studies conducted to date. [REDACTED]

## 6 STUDY POPULATION

### 6.1 Inclusion Criteria

In order to be eligible to participate in this study, an individual must meet all of the following criteria:

#### 1) Signed written informed consent

- a) Not applicable per Revised Global Protocol v01.
- b) Willing and able to complete all study-specific procedures and visits.
- c) Willing to participate in the study and sign the informed consent form (ICF) by participants (or legally acceptable representative).

#### 2) Type of Participant and Target Disease Characteristics

- a) Not applicable per Revised Global Protocol v01.
- b) **Not applicable per Protocol Amendment 03** - Participants taking sodium glucose cotransporter 2 (SGLT2) inhibitors, glucagon-like peptide-1 (GLP-1) receptor agonists, anti-obesity agents, or approved NASH treatment must have been on stable doses for at least 3 months prior to the liver biopsy used to confirm eligibility.
- c) Participants taking vitamin E at doses  $\geq$  800 IU/day must have been on stable doses for at least 6 months prior to the screening visit. If used, vitamin E must have been initiated prior to the liver biopsy used to determine eligibility.
- d) **Not applicable per Protocol Amendment 03** - Adequate DXA scan performed during screening confirmed by the central imaging facility prior to Randomization (see [Section 6.2](#)).
- e) **Not applicable per Protocol Amendment 03** - Liver biopsy performed within 6 months prior to the screening visit or performed during the screening period. A liver biopsy performed prior to ICF, if utilized for eligibility, must be available for central pathology reading prior to Randomization.

i) Liver biopsy consistent with NASH CRN Fibrosis Score Stage 4, as assessed by central pathology reading.

ii) Liver biopsy must either be consistent with steatohepatitis, as assessed by central pathology reading, OR, for liver biopsies without definite steatohepatitis, there should be some evidence of steatosis and/or ballooning and the following definition of NASH cirrhosis must be fulfilled:

(1) Absence of other causes of liver disease AND either of the following:

(a) At least 2 of the 3 following criteria:

(i) History of body mass index (BMI)  $\geq 30 \text{ kg/m}^2$

(ii) History of type 2 diabetes mellitus

(iii) History of hypertension AND/OR history of dyslipidemia

OR

(b) Previous histologic readings of steatohepatitis (for biopsies  $> 6$  months prior to screening visit) AND either history of BMI  $\geq 30 \text{ kg/m}^2$  OR history of type 2 diabetes mellitus.

NOTE: At least 80% of participants will be required to have definite steatohepatitis on the biopsy used to confirm eligibility.

f) Adequate DXA scan performed during screening and determined by the central imaging vendor prior to Randomization (see [Section 6.2](#)).

g) Liver biopsy performed within 12 months prior to the screening visit or performed during the screening period. A liver biopsy performed prior to ICF, if utilized for eligibility, must be available for central pathology reading prior to Randomization.

i) Liver biopsy consistent with NASH CRN Fibrosis Score Stage 4, as assessed by central pathology reading.

ii) Liver biopsy must either be consistent with steatohepatitis, as assessed by central pathology reading, OR, for liver biopsies without definite steatohepatitis, there should be some evidence of steatosis and/or ballooning and the following definition of NASH cirrhosis must be fulfilled:

(1) Absence of other causes of liver disease AND either of the following:

(a) At least 2 of the 3 following criteria:

(i) History of body mass index (BMI)  $\geq 30 \text{ kg/m}^2$

(ii) History of type 2 diabetes mellitus

(iii) History of hypertension AND/OR history of dyslipidemia

OR

(b) Previous histologic readings of steatohepatitis (in a past biopsy prior to the one utilized for eligibility) AND either history of BMI  $\geq 30 \text{ kg/m}^2$  OR history of type 2 diabetes mellitus.

NOTE: At least 80% of participants will be required to have definite steatohepatitis on the biopsy used to confirm eligibility.

h) Participants taking sodium glucose cotransporter 2 (SGLT2) inhibitors, glucagon-like peptide-1 (GLP-1) receptor agonists, anti-obesity agents, or approved NASH treatment must have been on stable doses for at least 3 months prior to screening.

### 3) Age and reproductive status

Investigators shall counsel WOCBP, and male participants who are sexually active with WOCBP, on the importance of pregnancy prevention, the implications of an unexpected pregnancy, and the potential of fetal toxicity occurring due to transmission of study drug, present in seminal fluid, to a developing fetus, even if the participant has undergone a successful vasectomy or if the partner is pregnant.

- The investigator shall evaluate the effectiveness of the contraceptive method in relationship to the first dose of study intervention.
- Local laws and regulations may require the use of alternative and/or additional contraception methods.

#### a) Female Participants

- i) Female participants ages  $\geq 21$  years to  $\leq 75$  years of age, inclusive, at the time of screening.
- ii) Not applicable per Revised Global Protocol v01.
- iii) WOCBP must have a negative highly sensitive serum or urine pregnancy test (minimum sensitivity 25 IU/L or equivalent units of human chorionic gonadotropin) within 24 hours prior to the following: start of study treatment and each dose of study treatment.
  - (1) If a urine test cannot be confirmed as negative (eg, an ambiguous result), a serum pregnancy test is required. In such cases, the participant must be excluded from participation if the serum pregnancy result is positive.
  - (2) Additional requirements for pregnancy testing during and after study intervention are located in [Section 2](#), SOA.
  - (3) The investigator is responsible for review of medical history, menstrual history, and recent sexual activity to decrease the risk for inclusion of a woman with an early undetected pregnancy.
- iv) Not applicable per Revised Global Protocol v01.
- v) A female participant is eligible to participate if she is not pregnant or breastfeeding, and at least one of the following conditions applies:
  - (1) Is not a WOCBP (female participants must have documented proof that they are not of childbearing potential)  
OR
  - (2) Is a WOCBP and is using a contraceptive method that is highly effective (with a failure rate of  $< 1\%$  per year), as described in [APPENDIX 4](#), during the intervention period and for at least 20 days after the last dose of study intervention and agrees not to donate eggs (ova, oocytes) for the purpose of reproduction for the same time period.
- vi) WOCBP must agree to follow instructions for highly effective method(s) of contraception, as defined in APPENDIX 4 and as described below and included in the ICF.
  - (1) WOCBP are permitted to use hormonal contraception methods (as described in APPENDIX 4)

(2) Women who are not of childbearing potential are exempt from contraceptive requirements

b) Male Participants

- i) Male participants ages  $\geq 21$  years to  $\leq 75$  years of age, inclusive, at the time of screening.
- ii) Male participants who are sexually active with WOCBP must agree to follow instructions for method(s) of contraception, as defined in [APPENDIX 4](#) and as described below.
- iii) Not applicable per Revised Global Protocol v01.
- iv) Not applicable per Revised Global Protocol v01.
- v) Not applicable per Revised Global Protocol v01.
- vi) Not applicable per Revised Global Protocol v01.
- vii) Not applicable per Revised Global Protocol v01.
- viii) Breastfeeding partners should be advised to consult their healthcare providers about using appropriate highly effective contraception during the time the participant is required to use condoms.
- ix) Azoospermic male participants are not exempt from contraceptive requirements and will be required to always use a latex or other synthetic condom during any sexual activity (eg, vaginal, anal, oral) with WOCBP, even if the participant has undergone a successful vasectomy or if the partner is pregnant.
- x) Male participants must be willing to and will be required to always use a latex or other synthetic condom during any sexual activity (eg, vaginal, anal, oral) with WOCBP; even if the participants have undergone a successful vasectomy or if their partner is already pregnant or breastfeeding. Male participants should continue to use a condom during the intervention period and for at least 20 days after the last dose of study intervention.
- xi) Male participants with a pregnant or breastfeeding partner must agree to remain abstinent from sexual activity or use a male condom during any sexual activity (eg, vaginal, anal, oral) even if the participants have undergone a successful vasectomy, during the intervention period and for at least 20 days after the last dose of study intervention.
- xii) Male participants must refrain from donating sperm during the intervention period and for at least 20 days after the last dose of study intervention.
- xiii) Female partners of male participants participating in the study should be advised to use highly effective methods of contraception during the intervention period and for at least 20 days after the last dose of study intervention in the male participant.

## 6.2 Exclusion Criteria

An individual who meets any of the following criteria will be excluded from participation in this study:

## 1) Target disease exclusions

- a) Other active causes of liver disease (eg, alcoholic liver disease, HBV infection [see [APPENDIX 7](#)]), chronic HCV infection [see [APPENDIX 7](#)], autoimmune hepatitis, primary biliary cholangitis, primary sclerosing cholangitis, drug-induced hepatotoxicity, Wilson disease, homozygous  $\alpha$ -1-antitrypsin deficiency, iron overload [with blood iron saturation  $> 50\%$ ], or hemochromatosis).
- b) Past or current evidence of hepatic decompensation (eg, ascites, variceal bleeding, hepatic encephalopathy, or spontaneous bacterial peritonitis).
- c) **Not applicable per Protocol Amendment 03** - Liver transplantation (past or planned).
- d) Not applicable per Revised Global Protocol v01.
- e) **Not applicable per Revised Global Protocol v02** - Model for End-stage Liver Disease (MELD) Score  $> 14$  at screening ([APPENDIX 6](#)). Participants who have a MELD Score  $> 14$  due to an isolated elevated INR and who are taking an anticoagulant known to prolong INR or who have Gilbert Syndrome and direct bilirubin  $\leq$  ULN may be included after discussion with the Medical Monitor.
- f) **Not applicable per Revised Global Protocol v02** - Evidence of HCC at screening based on serum alpha-fetoprotein (AFP) levels, as indicated below, or any imaging technique (eg, magnetic resonance imaging [MRI], computed tomography [CT], or ultrasound; based on local assessment):
  - i) AFP  $> 20$  ng/mL ( $> 16.5$  IU/mL) OR
  - ii) LI-RADS 3, 4, or 5 noted on the last historical CT or MRI, regardless of the AFP at screening. If screening ultrasound has a hepatic lesion  $\geq 10$  mm in size, the participant must have the last historical CT or MRI performed within 3 months prior to screening or a new CT or MRI can be performed.
- g) **Not applicable per Revised Global Protocol v02** - Child-Pugh Score  $> 5$  at screening ([APPENDIX 5](#)). Participants who have a Child-Pugh Score  $> 5$  due to an isolated elevated INR and who are taking an anticoagulant known to prolong INR, or who have Gilbert Syndrome and direct bilirubin  $\leq$  the ULN, may be included after discussion with the Medical Monitor.
- h) **Not applicable per Protocol Amendment 03** - MELD Score  $> 14$  at screening ([APPENDIX 6](#)). Participants with a MELD Score  $> 14$  with elevated total bilirubin and who have Gilbert Syndrome and direct bilirubin  $\leq$  ULN may be included after discussion with the Medical Monitor.
- i) **Not applicable per Protocol Amendment 03** - Evidence of HCC at screening based on (i) serum alpha-fetoprotein (AFP)  $> 20$  ng/mL ( $> 16.5$  IU/mL) or (ii) Liver Reporting & Data System^35 3, 4, or 5 as determined by historical CT/ MRI within 3 months prior to screening or from multiphasic CT/MRI of liver during screening.
- j) **Not applicable per Protocol Amendment 03** - Child-Pugh Score  $> 6$  at screening ([APPENDIX 5](#)). Participants with a Child-Pugh Score  $> 6$  with elevated total bilirubin and who have Gilbert Syndrome and direct bilirubin  $\leq$  the ULN, may be included after discussion with the Medical Monitor.
- k) Liver transplantation (past or planned during the study).

- l) MELD Score  $> 14$  at screening ([APPENDIX 6](#)). Exception: Participants with Gilbert Syndrome who have a MELD Score  $> 14$  with elevated total bilirubin, and direct bilirubin  $\leq$  ULN may be included provided that total bilirubin is  $< 4.0$  mg/dL.
- m) Evidence of HCC at screening based on (i) serum alpha-fetoprotein (AFP)  $> 20$  ng/mL ( $> 16.5$  IU/mL) or (ii) Liver Reporting & Data System^35 3, 4, or 5 as determined by historical computed tomography (CT)/magnetic resonance imaging (MRI) within 3 months prior to screening or from multiphasic CT/MRI of liver during screening. Both AFP and CT/MRI assessments will be required from all participants to determine eligibility.
- n) Child-Pugh Score  $> 6$  at screening ([APPENDIX 5](#)). Exception: Participants with Gilbert Syndrome who have a Child-Pugh Score  $> 6$  with elevated total bilirubin, and direct bilirubin  $\leq$  the ULN may be included, provided that total bilirubin is  $< 4.0$  mg/dL.

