Section 6.1: Inclusion Criteria	Stable dose of treatment requirements was updated to 3 months prior to screening.	Updated due to extension of historical biopsy to 12 months and requirement for stable dose to 15 months prior to screening will be very difficult.
Section 6.2: Exclusion Criteria and Section 8.1: Discontinuation from Study Treatment	Planned liver transplantation changed to planned during the study.	Updated to clarify timeframes of unacceptable liver transplantation.
Section 6.2: Exclusion Criteria	Removed required discussion with Medical Monitor related to MELD and Child-Pugh Score criteria.	Updated to align with local UK amendment, and to provide more objective guidance for investigators to make the eligibility determination of participants with Gilbert syndrome whose MELD and Child-Pugh Scores are elevated due to a benign cause of unconjugated hyperbilirubinemia without requiring consultation with the Medical Monitor.
Section 6.2: Exclusion Criteria	Clarification added that both serum AFP and historical CT/MRI will be required for Screening, and if either of the results meets the criteria the participant will be excluded from study.	Updated for clarification.
Section 6.2: Exclusion Criteria	Updated history of SARS-CoV-2 infection to history of severe COVID-19 disease and added timeframe for screening after mild and moderate infection.	Updated criteria to clarify specific timeframes for screening after COVID depending on the severity of the previous infection.
Section 6.2: Exclusion Criteria	History of significant weight gain/loss relative to the timing of the liver biopsy was removed, and any significant weight changes was updated to within 3 months of screening.	Removed due to extension of historical biopsy to 12 months and requirement for stable weight up to 15 months prior to screening will be very difficult.
Section 6.2: Exclusion Criteria	Exclusion criteria updates so that vaccines approved by regulatory agencies other than the United States Food and Drug Administration may also be considered for inclusion.	Updated to allow vaccines approved by other regulatory agencies.
Section 6.2: Exclusion Criteria	Exclusion criteria for laboratory results were updated that HbA1c could not be $\geq 9.5\%$ instead of 9.0%.	Revised to expand the study population.

[figure not shown]
SUMMARY OF KEY CHANGES TO THE REVISED PROTOCOL 03		

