### 4) Physical and laboratory test findings

- a) Evidence of organ dysfunction or any clinically significant deviation from normal in physical examination, vital signs, ECG, or clinical laboratory determinations beyond what is consistent with the target population.
- b) The participant's baseline laboratory test results include abnormal values considered to be clinically significant by the investigator.
- c) **Not applicable per Revised Global Protocol v02** - The participant's laboratory test results at screening include any of the following:
  - Albumin  $< 3.5$  g/dL

- INR > 1.4 (participants who have an INR > 1.4 and who are taking an anticoagulant known to prolong INR may be included after discussion with the Medical Monitor)
- ALT value  $\geq 5 \times$  the ULN
- AST value  $\geq 5 \times$  the ULN
- Total bilirubin > 1.5 mg/dL, unless participant has a diagnosis of Gilbert Syndrome and direct bilirubin  $\leq$  ULN
- Platelet count < 140,000/ $\mu$ L
- Hemoglobin A1c  $\geq 9.0\%$
- Serum vitamin A (retinol) > ULN

d) Glomerular filtration rate < 30 mL/min/1.73 m^2 according to the Modification of Diet in Renal Disease equation at screening.

e) Centrally-read DXA scan BMD T-Score of -2.5 or less at the femoral neck, total hip, or lumbar spine during screening (in participants 40 years of age or older).

f) **Not applicable per Protocol Amendment 03** - The participant's laboratory test results at screening include any of the following:

- Albumin < 2.8 g/dL
- INR > 2.2
- ALT value  $\geq 5 \times$  the ULN
- AST value  $\geq 5 \times$  the ULN
- Total bilirubin > 3.0 mg/dL, unless participant has a diagnosis of Gilbert Syndrome and direct bilirubin  $\leq$  ULN
- Platelet count < 85,000/ $\mu$ L
- Hemoglobin A1c  $\geq 9.0\%$
- Serum vitamin A (retinol) > ULN

g) The participant's laboratory test results at screening include any of the following:

- Albumin < 2.8 g/dL
- International normalized ratio (INR) > 2.2
- ALT value  $\geq 5 \times$  the ULN
- AST value  $\geq 5 \times$  the ULN
- Total bilirubin > 3.0 mg/dL, unless participant has a documented diagnosis of Gilbert Syndrome, provided that total bilirubin is < 4.0 mg/dL and direct bilirubin is  $\leq$  ULN
- Platelet count < 85,000/ $\mu$ L
- Hemoglobin A1c  $\geq 9.5\%$
- Serum vitamin A (retinol) > ULN

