**APPENDIX 5 CHILD-PUGH SCORING**

Parameter	Classification	Score
Bilirubin (Total) a	< 2 mg/dL (< 34.2 µmol/L)	+1
	2-3 mg/dL (34.2-51.3 µmol/L)	+2
	> 3 mg/dL (> 51.3 µmol/L)	+3
Albumin a	> 3.5 g/dL (> 35 g/L)	+1
	2.8-3.5 g/dL (28-35 g/L)	+2
	< 2.8 g/dL (< 28 g/L)	+3
International Normalized Ratio a	< 1.7	+1
	1.7-2.2	+2
	> 2.2	+3
Ascites	Absent	+1
	Slight	+2
	Moderate	+3
Encephalopathy	No encephalopathy	+1
	Mild to moderate (Grade 1-2)	+2
	Severe (Grade 3-4)	+3

a All laboratory parameters must be taken from the same blood draw.

Note: in the event of retesting of Child-Pugh Score, all laboratory parameters should be retested to allow for accurate calculations.

For the calculation of the Child-Pugh Score the sum of the scoring points from the 5 clinical parameters (total bilirubin, albumin, INR, ascites, and encephalopathy) corresponds to 1 of 3 categories:

Child-Pugh A = 5 to 6 points

Child-Pugh B = 7 to 9 points

Child-Pugh C =  $\geq$  10 points.

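### The Gilbert Syndrome exceptions to the Child-Pugh and MELD limits do not require bilirubin to be the reason the score is too high

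*Combined protocol and SAP*

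**What the plan says.** Section 6.2, criterion 1)n), excludes a Child-Pugh score above 6 at screening and then adds: "Exception: Participants with Gilbert Syndrome who have a Child-Pugh Score" above the limit may be included. Criterion 1)l) does the same for MELD above 14: "Exception: Participants with Gilbert Syndrome who have a MELD Score". In both, the link between the score and bilirubin is "with elevated total bilirubin, and direct bilirubin" at or below ULN, with total bilirubin under 4.0 mg/dL. The synopsis carries the same two exceptions.

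The summary of key changes for Amendment 03 explains this wording. It is meant to give investigators more objective guidance, without a Medical Monitor consultation, for Gilbert participants "whose MELD and Child-Pugh Scores are elevated due to a benign cause of unconjugated hyperbilirubinemia".

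The other fixed limits in Section 6.2 are in 4)g), which excludes "Albumin < 2.8 g/dL", "International normalized ratio (INR) > 2.2" and total bilirubin above 3.0 mg/dL "unless participant has a documented diagnosis of Gilbert Syndrome" (then below 4.0 mg/dL with direct bilirubin no higher than ULN); in 4)d), which excludes GFR below 30; and in 1)b), which excludes past or current decompensation. Appendix 5 gives the Child-Pugh points and Appendix 6 the MELD formula.

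**The concern.** The rationale is causal: the score is high because of a benign bilirubin trait, so it overstates the liver disease. The operative criteria ask only for coexistence. Every condition in the exception concerns bilirubin, and none asks whether albumin, INR or creatinine would take the score over the limit without it.

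Two people with the same albumin, INR and creatinine can therefore be treated differently because one of them has an unrelated benign trait. What is at stake is the definition of the enrolled population and consistent screening across sites. Appendix 9 describes the widening of the population, in Revised Protocol 02, as going from Child-Pugh A5 to A6. Section 9 allows no waivers or exemptions, so sites will apply the text as it stands.

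**Working it through.** The plan states no figure for this point, so there is none to reproduce. The check asks which scores remain possible under the fixed limits, and which still exceed the limit once bilirubin is neutralised.

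**Child-Pugh (Appendix 5).** Points available to a Gilbert participant:
- Bilirubin: 1 (below 2 mg/dL), 2 (2-3) or 3 (above 3, here below 4.0).
- Albumin: 1 (above 3.5 g/dL) or 2 (2.8-3.5); lower values are excluded by 4)g).
- INR: 1 (below 1.7) or 2 (1.7-2.2); higher values are excluded by 4)g).
- Ascites and encephalopathy: 1 each, because decompensation is excluded by 1)b).

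This gives 3 × 2 × 2 = 12 profiles, of which eight score above 6:

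| Bilirubin | Albumin | INR | Total | Total with bilirubin at 1 point |
|---|---|---|---|---|
| 1 | 2 | 2 | 7 | **7** |
| 2 | 1 | 2 | 7 | 6 |
| 2 | 2 | 1 | 7 | 6 |
| 2 | 2 | 2 | 8 | **7** |
| 3 | 1 | 1 | 7 | 5 |
| 3 | 1 | 2 | 8 | 6 |
| 3 | 2 | 1 | 8 | 6 |
| 3 | 2 | 2 | 9 | **7** |

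In five profiles bilirubin is what takes the score over 6, as the rationale intends. In three it is not: albumin and INR together already give 1 + 2 + 2 + 1 + 1 = 7, which Appendix 5 classes as B ("Child-Pugh B = 7 to 9 points").

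**MELD (Appendix 6).** MELD = 9.57 ln(creatinine) + 3.78 ln(bilirubin) + 11.20 ln(INR) + 6.43. At bilirubin 1.0 mg/dL the bilirubin term is zero.
- Bilirubin by itself: at 3.99 mg/dL with creatinine and INR both 1.0, 3.78 × ln(3.99) + 6.43 = 11.7. Bilirubin below 4.0 cannot pass 14 without help from INR or creatinine.
- An intended case: bilirubin 3.99, INR 1.4, creatinine 1.0 gives 15.4. Without the bilirubin term it is 15.4 − 5.2 = 10.2, so bilirubin is decisive.
- An unintended case: creatinine 1.2 and INR 2.1 with the bilirubin term at zero give 1.74 + 8.31 + 6.43 = 16.5.
- Thresholds with the bilirubin term at zero: INR above exp(7.57/11.20) = 1.97 at creatinine 1.0, or creatinine above exp(7.57/9.57) = 2.21 mg/dL at INR 1.0. The INR figure lies inside the 2.2 limit. For creatinine the only bound is GFR 30, and the equation is cited but not printed, so the highest creatinine allowed cannot be fixed from the documents.

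**Side by side.** Two people have creatinine 1.2, albumin 3.0 and INR 2.1, with no ascites or encephalopathy:
- No Gilbert Syndrome, bilirubin 1.0: Child-Pugh 7, MELD 16.5. Excluded on both.
- Gilbert Syndrome, bilirubin 2.0, direct bilirubin within ULN: Child-Pugh 2 + 2 + 2 + 1 + 1 = 8, MELD 16.5 + 2.6 = 19.1. Excluded on neither, although the scores without excess bilirubin are still 7 and 16.5.

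**The case against.** **The mismatch rests on an amendment summary.** A difference between a change log and current text is not in itself an error. But this entry gives the reason for the criteria now in force; it does not describe superseded text. A reader might also infer that Amendment 03 dropped a causal condition. It did not: the superseded 1)h) and 1)j) also spoke only of a score with elevated bilirubin. Amendment 03 added the 4.0 mg/dL cap and removed the Medical Monitor discussion.

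**Safeguards remain.** This stands. Inclusion is permitted, not required. Investigators can exclude under 2)a), 2)h), 2)q) (unsafe biopsy), 4)a), 4)b) and 6)c), and 2)a) also names the Medical Monitor. Anticoagulants are barred by 3)i), and Section 9.1.2 addresses prolonged INR before biopsy. These are matters of judgement, however, and the stated aim was more objective guidance.

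**Stronger readings the documents do not support:**
- *The exception lets in Child-Pugh B9 disease.* A total of 9 is possible, but it includes 3 bilirubin points, which the exception is meant to forgive. Without excess bilirubin points the maximum is 7.
- *Low albumin, raised INR or raised creatinine alone is enough.* For Child-Pugh, albumin and INR are both needed, since either alone gives at most 6. Albumin is not in MELD, and creatinine is not in Child-Pugh.
- *These participants fall outside the safety justification.* Section 3.2.2 recommends no dose adjustment in mild or moderate hepatic impairment, and Section 3.3.1 describes an acceptable safety profile in both. The hepatic-impairment study gave single doses, to 8 people with moderate impairment, and the documents do not map its grades to Child-Pugh classes. Even so, the text is not confined to Child-Pugh A.
- *Raised INR at biopsy is peculiar to this exception.* A participant without Gilbert Syndrome and with INR 1.9, creatinine 1.0 and bilirubin 1.0 has MELD 13.6 and passes that limit.
- *A trivial bilirubin rise, say 1.3 mg/dL, triggers the exception.* That assumes a ULN below 1.3; the documents give none.

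**Conclusion.** The point holds as a gap between rule and purpose. The exceptions require coexistence with elevated bilirubin where the rationale requires cause. Three of the eight exempt Child-Pugh profiles, and any MELD above 14 built from INR and/or creatinine without bilirubin, pass the score criteria although bilirubin is not the reason for the excess.

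The practical size is probably small. It needs Gilbert Syndrome together with independently abnormal laboratory values, in someone without decompensation whom the investigator still considers suitable. The documents give no Gilbert prevalence, so no count can be derived. No effect on power or on the primary analysis is shown or claimed. The case for acting is that screening should follow the sponsor's own stated reason at every site, and that the change is cheap.

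Assumptions: MELD is unrounded and taken as printed in Appendix 6, the creatinine values are illustrative, and bilirubin 2.0 mg/dL is taken to be above ULN.

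**What to change.** Reconcile criteria 1)l) and 1)n) and the synopsis with the Amendment 03 rationale. State in each place that the exception applies only where the bilirubin component is what takes the score over the existing limit.

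One way to express this with the sponsor's own thresholds is to recalculate the score with bilirubin neutralised (1 Child-Pugh point; MELD bilirubin term at zero) and compare it with 6 and 14. The choice of final rule is the sponsor's.

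The cost is a sentence in each place at the next amendment and a second score from values already collected at screening, with no return to Medical Monitor consultation. The downside is that a very few Gilbert participants with independently abnormal INR, albumin or creatinine would no longer be eligible.
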